8.3.5 Method of Continuing already Randomized Subject from Previous study

Once a SIN has been assigned, that number must not be used again for any other subject (e.g., when a subject is withdrawn from the study, that subject's SIN must not be reused for any other subject). See [Section 9](#).

8.3.6 Blinding

All attempts will be made to keep the investigative site staff and subjects blinded to the study treatment from study RD.06.SPR.112199 throughout the study. Members of the study center staff, including the procedure operator, will not have access to the randomized treatment assignment of subjects in RD.06.SPR.112199. It would be extremely unlikely for a situation to occur in which the blind would need to be broken during this study. The Investigator or sub-investigator should consult with the medical monitor and the Sponsor in cases where it be required to break the blind.

When the blinding code is broken, the reason must be fully documented. If the code is broken by the Investigator, the subject must be withdrawn from the study. The reporting requirements for unblinding are the same for reporting an SAE. See also [Section 9.2.1.3](#)

The randomization code will remain blinded to all study sites and study team members until completion of the study and after the study database has been locked. Initial treatment period results will be analyzed after all subjects have either completed Visit 6 , or have withdrawn or been discontinued from the study before Visit 6. However, personnel from sponsor, CRO, and investigational sites directly involved with the ongoing conduct of the study will not have access to any information that may lead to unblinding for the ongoing recurrence evaluation during the follow-up study.

8.3.7 Prior and Concomitant Therapy

Concomitant therapies/medications are defined as follows:

- Any existing therapies ongoing at the time of the screening visit,
- Any changes to existing therapies (such as changes in dose, formulation, or application frequency) during the course of the study, or
- Any new therapies received by the subject since the screening visit

The following 2 categories are to be considered for prior and concomitant therapies:

- Drugs/Therapies include but are not limited to prescription, over-the-counter, birth control pills/patches/hormonal devices, vitamins, moisturizers, sunscreens, herbal medicines/supplements, and homeopathic preparations.
- Medical and surgical procedures (e.g., phototherapy, exodontia). Procedures whose sole purpose is diagnosis (non-therapeutic) are not included.

Prior and concomitant therapies for drugs/therapies or for medical/surgical procedures are to be recorded in the appropriate eCRF.

Concomitant therapies are to be recorded, reviewed, and updated at each visit.

Any new concomitant therapy or modification of an existing therapy may be linked to an AE. In such cases, a corresponding AE form should be completed to account for the new therapy or change in therapy, in which case the medication will be linked to an item in the subject's medical history.

The therapies listed in [Table 2](#) are considered prohibited in the treatment areas because they may interfere with the lesion assessments.

Table 2: Forbidden Treatments in Treatment Area

Treatment(s)
Topical: 5-fluorouracil, diclofenac, imiquimod, retinoids, alpha-hydroxy acid, salicylic acid ointment, ingenol mebutate
Surgical: elliptical excision, excision and reconstructive surgery, Mohs' micrographic surgery, chemical peels/chemosurgery, cryosurgery, dermabrasion
Photodynamic therapy
Electrocoagulation therapy
Radiotherapy of the skin
Laser therapy
Investigative therapies for actinic keratosis
Systemic retinoids
Immunosuppressive agents such as glucocorticoids, cytostatic agents, antibodies, drugs acting on immunophilins, interferon, TNF binding proteins, mycophenolate mofetil, or biologics

In case the subject is using topical therapy listed in [Table 2](#) on other areas than on the documented lesions, the Investigator will remind him/her to pay strict attention to not apply any of these therapies on the treatment areas.

If prohibited therapies become a necessary treatment for the safety or best interest of the subject, the medical monitor should be notified to discuss possible alternatives prior to administration of a prohibited therapy. It is also possible that the use of prohibited therapies may result in early termination of a subject.

If a subject receives prohibited therapy during the clinical study, the medical monitor should be notified to discuss the significance and the modalities to be used for the subject to continue in the clinical study.

8.4 Duration of Subject Participation

The expected duration for each subject's participation in the study will be approximately 40 weeks.

8.4.1 Early Termination Visit

Subjects may discontinue from the study at any time.

Subjects who prematurely discontinue from the study should undergo final study assessments.

8.5 Unscheduled Visit

The subject should be reminded to adhere to the study schedule. Unscheduled visits are defined as visits occurring outside of the visit window.

Assessments to be conducted at the unscheduled visit will depend on the reason for the visit and will be conducted at the discretion of the principal investigator. Any of the procedures/assessments listed in [Section 8.1.2](#) may be conducted, but not all are required.

9 STUDY ASSESSMENTS

A written, signed Informed Consent Form (ICF), and Health Insurance Portability and Accountability Act (HIPAA) authorization is required before any study-related procedures are performed.

Upon provision of the signed ICF, each subject will be assigned a unique different SIN from the SIN in protocol RD.06.SPR.112199. For the duration of the clinical study, the subject will be identified using the new SIN in all documentation and discussion for this protocol.

9.1 Efficacy Assessments

Evaluations are to be performed by the same Investigator for a given subject throughout the study, whenever possible. The Investigator is to remain blinded to the study treatment from study RD.06.SPR.112199.

9.1.1 Lesion Response

The lesions treated in the pivotal trial will be evaluated for reoccurrence. Any lesions that have recurred will be evaluated for severity according to the grading scale in [Table 3](#)

Table 3: Lesion Severity Grade Scale

Grade	Severity	Description
Grade 1	Mild	Slightly palpable, better felt than seen
Grade 2	Moderate	Moderately thick, easily felt and seen
Grade 3	Severe	Very thick and/or obvious actinic keratoses

The Investigator will be asked at Visits 2 and 3/ET to identify each lesion treated previously, and the lesion response as a CR or a non-CR, as described in [Table 4](#).

Table 4: Lesion Response

Response	Score	Description
Complete response (CR)	1	Complete disappearance of the lesion, visually and by palpation
Non complete response (non-CR)	0	Non-complete disappearance of the lesion

If all of the treated lesions in the treatment area are assessed to be CR at Visits 2 and 3 of this study (26 and 52 weeks after the last DL-PDT session), the subject will be assessed as a subject CR and will be deemed to have no recurrence. If any of the treated lesions in the treatment area are assessed to be non-CR, those lesions are recurrences; the subject will be assessed as a non-complete responder or deemed as a subject recurrence.

9.2 Safety Assessments

Safety assessments will be conducted for all subjects at Visit 1 (upon signing of the ICF) and at every subsequent visit.

Adverse events (AEs), Treatment-emergent AEs (TEAEs), related to the study treatment in study RD.06.SPR.112199, and serious AEs (SAEs) will be recorded during each visit, should they occur.

Adverse Event Definition

An AE is defined as any untoward medical occurrence in a clinical study, in which a subject is administered a medicinal product that does not necessarily have a causal relationship with this treatment. An AE can therefore be any unfavorable and unintended sign (including an abnormal laboratory finding), symptom, or disease temporally associated with the use of a medicinal product, whether or not it is related to the medicinal product. This includes an exacerbation of pre-existing conditions or events, intercurrent illnesses, drug interaction, or the significant worsening of the indication under investigation, that is not recorded elsewhere in the eCRF under specific efficacy assessments.

Note(s):

- Any new sign or symptom reported by the subject that appears after accidental or intentional overdose or misuse should be reported as an AE.
- Whenever possible, a diagnosis should be reported on the AE form, instead of signs, symptoms, or abnormal laboratory values.
Pregnancy is not to be considered an AE
- Each new episode of a chronic disease (e.g., hay fever, allergy) from the time the ICF is signed should be reported as a new AE.

The Investigator or designee will report all AEs that occur from the time the ICF is signed until the end of the study. The sponsor/CRO should be informed if the Investigator becomes aware of any safety information that appears to be related to the study treatment of study RD.06.SPR.112199, even after the subject has completed the clinical study.

At each post-enrollment visit, the Investigator (or sub-investigator) will question the subject about his/her experiencing of AEs, using an open non-persuasive question to elicit reporting of AEs (for example, “Have you noticed any change in your health since the last visit?”). Directed questioning and examination will then be performed as appropriate.

Any AE occurring during the AE reporting period will be recorded immediately in the source document and described on the Adverse Event Form (“AE Form”) along with the date of onset, seriousness, severity, relatedness or causality and outcome, without omitting any requested and known information. Additional information will be requested under certain circumstances.

Adverse events assessed as related to the study treatment from the previous study will be monitored until they have resolved or reached a stable condition. Other AEs will be monitored until the last visit if they have not resolved or reached a stable condition. If not resolved at time of LTFU study completion, sites will continue to contact patient on a regular basis until resolved or stable.

The Investigator will obtain and maintain all pertinent medical records in the subject's files, information and medical judgment from colleagues who assisted in the subject's oversight. If necessary, the Investigator will contact the subject's personal physician or hospital staff to obtain further details.

Assessment of Severity

Each AE will be assigned a category by the Investigator as follows:

Mild:	An AE that is easily tolerated by the subject, causes minimal discomfort, and does not interfere with everyday activities.
Moderate:	An AE that is sufficiently discomforting to interfere with normal everyday activities; intervention may be needed.
Severe:	An AE that prevents normal everyday activities; treatment or other intervention usually needed.

If there is a change in severity of an AE, it must be recorded as a separate event.

Assessment of Causality

The Investigator will have determined that there is a reasonable causal relationship between the occurrence of the AE, and exposure to the study drug (i.e., MAL cream or vehicle cream) and/or study procedure (e.g., illumination, blood sample collection) in study RD.06.SPR.112199.

For AEs arising during this study, medical judgment should be used to determine the relationship, considering all relevant factors including the pattern of the reaction, temporal relationships, relevant medical history, and confounding factors such as co-medication or concurrent diseases.

The expression "reasonable causal relationship" is meant to convey in general that there are facts or arguments to suggest a causal relationship (ICH E2A, Section IIIA 1).

The relationship assessment for an AE is to be completed using the following definitions as a guideline for all AEs occurring during this clinical study:

Reasonable possibility:

According to the reporting Investigator, there is a reasonable possibility (i.e., suggestive evidence or arguments) that there is a causal relationship irrespective of the dose administered:

- Between the study drug (methyl aminolevinulate hydrochloride 16.8% cream or vehicle cream) and the AE, and/or

- Between the clinical study protocol procedure (e.g., topical background therapy, blood sample collection) and the AE

No Reasonable Possibility:

No suggestive evidence or arguments can be identified regarding a causal relationship between the study drug or the clinical study protocol procedure and the AE.

Follow-up of Adverse Events

All Investigators should follow-up with subjects with related AEs until the event is resolved or until, in the opinion of the Investigator, the event is stabilized or determined to be chronic. Details of AE resolution must be documented in the eCRF.

Documentation and Reporting of Adverse Events

Adverse events should be reported and documented in accordance with the procedures outlined below. All AEs occurring during the study must be documented on the relevant eCRF pages. The following data should be documented for each AE:

- Description of the symptom/event
- Classification of “serious” or “not serious”
- Severity
- Date of first occurrence and date of resolution (if applicable)
- Other action taken
- Causal relationship
- Outcome of event (unknown, recovered, not yet recovered, recovered with sequelae, death [with date and cause reported])

9.2.1.1 Serious Adverse Events

An SAE is any untoward medical occurrence or effect that, at any dose,

- Results in death.
- Is life-threatening (an AE is life-threatening if the subject was at immediate risk of death from the event as it occurred, i.e., it includes a reaction that might have caused death if it had occurred in a more serious form).
- Requires or prolongs inpatient hospitalization. (Complications occurring during hospitalization are AEs and SAEs, if they cause prolongation of the current hospitalization. Inpatient hospitalization is considered to have occurred if the subject has had to stay for a night at the hospital. The criterion for prolongation of hospitalization is also defined as an extra night at the hospital. Hospitalization may not constitute sufficient grounds to be considered as an SAE, if it is solely for the purpose of diagnostic tests [even if related to an AE], elective hospitalization for an intervention that was already planned before subject enrollment in the clinical study, admission to a day care facility, social admission [e.g., if the subject has no place to sleep], or administrative admission [e.g., for a yearly examination].

The details of such hospitalizations must be recorded on the medical history or physical examination eCRF.)

- Results in persistent or significant disability/incapacity. (An AE is incapacitating or disabling if it results in a substantial and/or permanent disruption of the subject's ability to carry out normal life functions.)
- Results in a congenital anomaly/birth defect.
- An important medical event that may not result in death, be life-threatening, or require hospitalization, may be considered an SAE when, based upon appropriate medical judgment, the event may jeopardize the safety of the subject, and may require medical or surgical intervention to prevent 1 of the outcomes listed above in this definition. Examples of such events are intensive treatment in an emergency room or at home for allergic bronchospasm, blood dyscrasias, or convulsions that do not result in hospitalization.

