9.2.1.3 Procedure for Reporting a Serious Adverse Event

For any SAE occurring during the clinical study, regardless of whether or not related to the study drug and/or procedure, the Investigator must:

1. Take prompt and appropriate medical action, if necessary. The safety of the subject is the first priority.
2. Ensure that the event is evaluated as an SAE. Immediately notify (**within 24 hours of receipt of the event**) the PPD Safety and Pharmacovigilance group of an SAE report, by email or fax:

Fax Number: PPD

Safety email: PPD

Note: Immediate SAE reporting is required by the Investigator if it occurs during the clinical study, whether or not the event is considered to be related to the investigational product. The demographics, medical history, drugs/therapies, and medical and surgical procedures forms must also be available for review in the eCRF, at that time.

3. Send any relevant information or anonymized medical records to the PPD Safety and Pharmacovigilance group (see contact details above), within 24 hours of receipt of this relevant information.
4. Monitor and record the progress of the event until it resolves or reaches a stable condition, with or without sequelae. For all additional follow-up evaluations, complete an updated SAE report **within 24 hours** of receipt of the updated information.
5. Obtain and maintain in the subject files all pertinent medical records, information, and medical judgments from colleagues who participate in the treatment and follow-up of the

subject. If necessary, contact the subject's personal physician or hospital staff to obtain further details.

6. When the outcome of the event is known, complete an updated SAE report, if appropriate.
7. Prompt notification of SAEs by the Investigator is essential so that legal obligations and ethical responsibilities toward the safety of subjects are met. The Sponsor has a legal responsibility to notify both the local regulatory authority and other regulatory agencies about the safety of a product under clinical investigation. The Sponsor or its delegate (i.e., the CRO) will comply with country-specific regulatory requirements relating to safety reporting to regulatory authorities, Institutional Review Board (IRB)/Independent Ethics Committee (IEC) and Investigators. Investigator safety reports are prepared for SUSARs according to local regulatory requirements, and are forwarded to Investigators as necessary.

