5.2.1. Adverse Events

Adverse events (AEs) will be recorded during each visit (Visits 1, 2 and 3) and during telephone call.

An AE is defined as any untoward medical occurrence in a clinical study, in which a subject is administered a medicinal product that does not necessarily have a causal relationship with this treatment. An AE can therefore be any unfavorable and unintended sign (including an abnormal laboratory finding), symptom, or disease temporally associated with the use of a medicinal (investigational) product, whether or not it is related to the medicinal (investigational) product. This includes an exacerbation of pre-existing conditions or events, intercurrent illnesses, drug interaction, or the significant worsening of the indication under investigation, that is not recorded elsewhere in the eCRF under specific efficacy assessments.

Refer to the study protocol for further details about AEs definition and management.

This document is confidential.

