9.11.1. Adverse Events Analysis

Treatment-emergent AEs are defined as those AEs occurring after the first administration of study treatment until the last study visit from study RD.06.SPR.112199 and as all AEs in this study RD.06.SPR.115230.

All treatment-emergent AEs will be listed in a by-subject listing which will include both the term reported on the eCRF (verbatim term) and the MedDRA System Organ Class and Preferred Term. Relative start and stop days will be included along with the actual onset and resolution dates.

If relationship is missing the closest relationship, i.e. "Related" will be imputed. If severity is missing the greatest severity, i.e. "Severe", will be imputed.

A summary table of TEAEs will be provided for each of the following for the safety population by treatment group and overall:

- Number and percentage (n, %) of subjects with any TEAE and frequency of TEAEs overall and by System Organ Class and Preferred Term;
- Number and percentage (n, %) of subjects with any TEAE by closest relationship to study drug and frequency of TEAEs by closest relationship to study drug;
- Number and percentage (n, %) of subjects with any TEAE by closest relationship to study procedures and frequency of TEAEs by closest relationship to study procedures;
- Number and percentage (n, %) of subjects with any TEAE related to the study drug and frequency of TEAEs related to the study drug by System Organ Class and Preferred Term;
- Number and percentage (n, %) of subjects with any TEAE related to the study procedures and frequency of TEAEs related to the study procedures by System Organ Class and Preferred Term;
- Number and percentage (n, %) of subjects with any TEAE by greatest severity and frequency of TEAEs by greatest severity overall and by System Organ Class and Preferred Term;
- Number and percentage (n, %) of subjects with any TEAE leading to study discontinuation and frequency of TEAEs leading to study discontinuation.

A summary table of serious TEAEs will be provided for each of the following in the safety population by treatment group and overall:

- Number and percentage (n, %) of subjects with any Serious TEAE and frequency of Serious TEAEs overall and by System Organ Class and Preferred Term;
- Number and percentage (n, %) of subjects with any Serious TEAE by closest relationship to study drug and frequency of Serious TEAEs by closest relationship to study drug;

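### The protocol's definition of a life-threatening SAE contradicts itself, so the same event can be classed as serious at one site and not at another

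*Protocol*

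**What the plan says.** Protocol 9.2.1.1 lists the conditions that make an adverse event serious. For the life-threatening condition, the explanation in parentheses begins "an AE is life-threatening if the subject was at immediate risk of death from the event as it occurred" and continues "i.e., it includes a reaction that might have caused death if it had occurred in a more serious form". The last item in the list is a separate route for events that meet none of the main outcomes: "An important medical event that may not result in death, be life-threatening, or require hospitalization, may be considered an SAE". That route depends on medical judgment that the subject may be in jeopardy and may need intervention to prevent one of the listed outcomes.

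The classification has consequences elsewhere:

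- Protocol 9.2 (documentation of adverse events) requires each AE to be recorded as serious or not serious.
- Protocol 9.2.1.3 requires notification within 24 hours whether or not the event is related: "Immediate SAE reporting is required by the Investigator if it occurs during the clinical study".
- SAP 5.2.1 defines an AE but not an SAE, and defers to the protocol: "Refer to the study protocol for further details about AEs definition and management".
- SAP 9.11.1 counts every AE in this follow-up study as treatment-emergent. It tabulates, by treatment group and overall, "subjects with any Serious TEAE and frequency of Serious TEAEs overall and by System Organ Class and Preferred Term", followed by further serious TEAE summaries.

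**The concern.** The abbreviation *i.e.* presents the second half of the criterion as a restatement of the first. It is not one. The first half asks what risk the event carried when it happened. The second asks what a worse version of it might have done. An event can fail the first test and pass the second.

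This is an operative rule, because the serious flag drives expedited reporting and fills the serious TEAE tables. Those tables serve the secondary objective, long-term safety (Protocol 7.2). About 60 centers are planned (Protocol synopsis), and an investigator who follows either half is following the protocol. The same event could therefore be serious at one center and not at another, and the tables would not show which rule was used.

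**Working it through.** No sample size, error rate or event count enters this point, and the documents give no figure to reproduce. The check is a comparison of text, with one division for scale.

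**1. The two halves side by side** (Protocol 9.2.1.1)

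| | Test applied | Event with no immediate risk of death, but conceivably fatal if worse |
|---|---|---|
| First half | Actual risk from the event as it happened | Not life-threatening |
| *i.e.* clause | Possible death in a more serious form | Life-threatening |

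The results differ, so the clause cannot be a restatement. With *does not include* in place of *includes*, both rows give the same answer. A dropped negation is the natural explanation.

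**2. Does the rest of the list fit either reading?** The important-medical-event item presupposes that some worrying events are not life-threatening and enters them only on judgment. If the hypothetical clause governed, many of these would already be serious without that judgment, and the item would lose much of its purpose. The structure of the list therefore supports the actual-risk test.

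**3. Does any other text settle it?** The severity scale in Protocol 9.2 grades mild, moderate and severe, which is not seriousness. SAP 5.2.1 refers back to the protocol. No other readable section restates the criterion.

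**4. Which events could be affected?** Only those that are serious through no other route. A fatal event, or one with an inpatient stay that meets the hospitalization condition, is serious under either half. The summary of serious TEAEs leading to death is thus not exposed.

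**5. Scale.** Protocol 8.1 anticipates about 111 MAL and 19 vehicle subjects. The change in the percentage of subjects with a serious TEAE for one reclassified subject is 100 × 1/n:

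- MAL: 100 × 1/111 = 0.9 percentage points
- Vehicle: 100 × 1/19 = 5.3 percentage points

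These are shifts per subject. They do not predict how many subjects would be reclassified, which would need AE and SAE rates that neither document gives.

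**6. Reach.** SAP 9.11.1 also counts treatment-emergent events from RD.06.SPR.112199. Those were classified under that study's protocol, which is not available here, so the tables may combine events classified under two definitions.

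**The case against.** The strongest reply is that the sentence is a slip with little practical effect.

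- **The first half can be read as controlling.** Since *i.e.* introduces an explanation, an investigator may treat the actual-risk test as the rule. Protocol 11.3 requires training on the protocol, and 12.3 requires conduct under GCP and ICH guidelines. If every site does this, no event is reclassified.
- **The clause speaks of a reaction, not any AE.** Protocol 9.2.1.5 uses *adverse reaction* for a response related to study drug. On that sense the clause is narrow here: nothing is administered, and Protocol 9.2.1.4 puts the start of this study 12 weeks and more than 7 half-lives after exposure. The protocol does not define *reaction* on its own, so this does not decide the matter.
- **The effect on conclusions is limited.** There is no formal test (SAP 9.1.7), sites are blinded, the same wording applies to both arms, and any error is towards over-reporting. SAP 9.11.1 lists seven summaries of all TEAEs that do not use the serious flag, and requires a listing of all serious AEs in which individual events can be inspected.

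All of this limits the consequences, and it rules out any claimed inflation factor. It does not remove the contradiction. Relying on sites to disregard half of a written rule does not make that rule consistent, and blinding does not make different sites apply the same half.

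**Conclusion.** The definition is wrong as written and should be corrected. The contradiction lies within one sentence, is certain, and is not repaired elsewhere. The consequences are possible rather than established: some events classed as serious that need not be, some unneeded 24-hour reports, and serious TEAE tables built on mixed rules. Their size cannot be estimated from the documents, and the lower end is zero. The shifts of 0.9 and 5.3 points per subject assume the anticipated 111 and 19 subjects and serve only as scale. The efficacy endpoints are unaffected.

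A reader might infer that ordinary AEs will become SAEs in large numbers, or that the serious TEAE proportion will be several times too high. The documents do not support this: it requires literal use of the second half at most sites, a broad sense of *reaction*, and AE rates that are nowhere stated. A reader might also infer that the long-term safety objective as a whole is compromised. The all-TEAE summaries do not depend on the serious flag, so that does not follow.

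**What to change.** In Protocol 9.2.1.1, change *it includes* to *it does not include*, so that the clause agrees with the *as it occurred* test, and notify all sites.

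Before lock, the sponsor's safety group should read this study's SAE reports and the listing of serious AEs and pick out any event that appears serious only under the hypothetical clause. The AE data fields listed in Protocol 9.2 show a serious or not-serious flag but not the criterion met, so the event descriptions have to be read; a filter on that flag is not enough. The safety group should query the investigator on each such event and leave the classification to the investigator. If the interim analysis (Protocol 10.1.5, SAP 9.9) uses an earlier data cut, the same review is worth doing for that cut.

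Events carried over from RD.06.SPR.112199 are outside this correction. A footnote to the serious TEAE tables can say that they were classified under that study's protocol.

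The cost is a one-phrase amendment with its IRB submission, a site notice, and a desk review of this study's SAEs. No assessment, endpoint or analysis method changes.
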